10.3 Study Endpoints

10.3.1 Primary Endpoint

Efficacy

- Proportion of responders at 6 months post system activation as demonstrated by ≥50% improvement in average number of urgency related incontinence episodes, measured by 7-day Patient Voiding Diary.
 - Overall study success criteria is defined as a lower 97.5% confidence bound for a single binomial proportion of >50% patient success at 6 months

Safety

• Incidence of adverse events from implantation to 12-months post-activation.

10.3.2 Secondary Endpoints

Bluewind will test three secondary endpoints. In order to control type I error of the family of secondary objectives at 5%, secondary objective hypothesis testing will only occur upon rejection of the primary objective null hypothesis.

- Proportion of subjects with ≥10 points (MID) improvement in HRQL (based on OAB-q) at 6 months post system activation
- Proportion of responders at 12 months post system activation as demonstrated by ≥50% improvement in either average number of urgency related incontinence episodes or average number of severe/large urgency related incontinence episodes, as measured by 7-day Patient Voiding Diary.

Number	Revision / Date	Page
G02-CLP-0002_US	Rev. 08 / 27 July 2021	30 of 75

 Proportion of responders at 6 months post system activation as demonstrated by ≥50% improvement in the average number of moderate-severe urgency episodes PPIUS degree 3,4 or <8 voids/day

10.3.3 Other Endpoints

The following endpoints will be assessed as other endpoints for the 6-, 12-, 24- and 36-months post activation, without formal hypothesis testing and type I error control.

- Incidence of procedure or device related adverse events from 12- to 36-months post activation
- Patient Global Impression of Improvement (PGI-I) score
- Treatment Benefit, Satisfaction, and Willingness to Continue (BSW)
- Reduction in the average number of severe/large urgency related incontinence episodes
- Improvement in OAB-q (HRQL and symptoms severity).
- Changes in the following OAB symptoms as measured by voiding diary compared to baseline:
 - Reduction in the number of micturition episodes.
 - o Reduction in the number of urgency related incontinence episodes.
 - Reduction in degree of urgency prior to void on Patient Perception of Intensity of Urgency Scale (PPIUS) from 0-4.
 - Reduction in severity of incontinence episodes (amount leaked).
- Proportion of dry subjects following treatment with the RENOVA iStim System as measured by 3
 consecutive days of a patient voiding diary
- Assessment of fecal incontinence symptoms in patients suffering from mixed fecal and urine incontinence
- Patient compliance with treatment
- Duration from treatment initiation to symptoms improvement (in subset of patients who stopped treatment after completing the 12-month visit and started again when consented for the long-term follow-up).
- Device usage

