7.2 Clinical experience with BlueWind RENOVA™ System

The company performed a pilot study to evaluate the use of the BlueWind System in the treatment of patients with overactive bladder with or without urgency urinary incontinence. The study was conducted in four European sites; two in the Netherlands and two in the UK. A total of 36 patients were sub-grouped as followed:

¹ Previous pre-clinical and clinical testing were performed on the first generation of the device. More detailed information is provided in the IB

Number	Revision / Date	Page
G02-CLP-0002_US	Rev. 08 / 27 July 2021	25 of 75

- Patients with no previous treatment with percutaneous tibial nerve stimulation (PTNS) [de novo patient group] and
- Patients with a documented success on PTNS therapy [prior-PTNS group]

Each subject served as his or her own control and evaluations were performed after 3 and 6-months of stimulations, compared to baseline.

The primary endpoint was safety and the secondary endpoints assessed the performance of the system using parameters collected from 3-day voiding diary and a quality of life questionnaire (OAB-q) and were defined as follows:

Primary Endpoints

The incidence of serious adverse events (system and/or procedure related)

Secondary Endpoints

- Six-month clinical improvement compared to baseline was measured by the effect of BlueWind Medical's therapy on the treatment of the following symptoms:
 - Number of voids/day
 - Volume voided/void
 - o Number of urgency leaks per day
 - Degree of urgency prior to void

In the presence of urgency incontinence, the following evaluations were performed:

- Leaking episodes/day
- Severity of leaking episodes (scale of 0-3; 0-no leak; 1-drops; 2-small amount; 3-large amount)
- Absorbent pads used due to leaking/day
- Quality of Life Questionnaire OAB-q

An analysis of 6-months clinical performance success was based on voiding diary parameters, where success was defined as a decrease of ≥50% in urgency frequency (UF) and urgency urinary incontinence (UUI) symptoms (voids/day or number of episodes with degree of urgency >2 from baseline; or a return to normal voiding frequency i.e. <8 voids/day for the UF group; and leaks/day for the UI group). As commonly defined in the literature, for the UUI population, dry subjects (no episodes of leakage) were considered as 100% clinical improvement.

Study Procedure

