10.7 Eligibility Criteria

10.7.1 Inclusion Criteria

1. Signed written informed consent.

Number	Revision / Date	Page
G02-CLP-0002_US	Rev. 08 / 27 July 2021	32 of 75

- 2. Female aged 18 or greater (21 or greater in the US), with no plans to become pregnant during the trial; if of bearing potential, negative pregnancy test and if sexually active, using acceptable contraception.
- 3. Subject who is mentally competent with the ability to understand and comply with the requirements of the study.
- 4. Diagnosis of UUI demonstrated on a 7-consecutive days voiding diary defined as a minimum of nine (9) leaking episodes associated with urgency, with at least one episode per day for 5 days.
- 5. More than or equal to 6 months history of UUI diagnosis
- 6. Subject with inadequate response to any of the following conservative treatments (i.e. dietary restriction, fluid restriction, bladder training, behavioral modification, pelvic muscle training, biofeedback, etc.) and pharmacologic treatment.
- 7. If used, subjects should be on stable dose of antimuscarinics and/or beta-3 adrenergic agonists for at least 3 months prior to baseline and agree to remain on stable medication consumption until the 12-month follow-up visit.
- 8. If used, subjects should be on a stable dose of tricyclic antidepressants, Selective Serotonin Reuptake Inhibitors (SSRI) and Serotonin-Norepinephrine Reuptake Inhibitors (SNRI) for at least 3 months prior to baseline.
- 9. Subjects with positive tibial nerve motor or sensory response tested via physical/neurological examination.
- 10. Subjects with normal renal function defined by GFR of 50 ml/min or more
- 11. Leg circumference of no less than 20 cm and no more than 30 cm at implantation site (i.e. 5cm above the medial malleolus).
- 12. Subject agrees to attend all follow-up evaluations and is willing and capable to completely and accurately fill out voiding diaries and questionnaires and is willing to complete required exams and tests.

The following inclusion criteria will be re-evaluated for patients who completed 12-months follow-up and exited the study:

1. Subject who is mentally competent with the ability to understand and comply with the requirements of the study.

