11.4.5 BlueWind RENOVA iStim™ System Follow Up Visits – Visits 4-8

Patients will attend the clinic at 1-, 3-, 6-, 9- and 12-months post system activation. Patients will be asked to fill in an electronic voiding diary (a 3-day diary at the 1-, 3- and 9-months post activation visits and a 7-day diary at the 6- and 12-months visits), immediately prior to every follow-up visit. Only after electronic diary information is entered to the EDC the tentatively scheduled visit will be confirmed.

Patients may receive several treatment programs to choose from based on treatment effect and comfort and accordingly may be asked to fill a voiding diary after each change.

During these visits, patients will be asked about their urinary symptoms, discomforts that might have been felt or other physiological or technical problems that might have arisen. Physical examination will be performed and patients will be asked to submit a sample of urine for urinalysis at each follow-up visit. If the urinalysis or the patient's symptoms suggest urinary tract infection, urine sample will be sent for culture and sensitivity. If culture results suggest urine tract infection, follow-up visit will be re-scheduled for after treatment.

Adverse events will be recorded in the patient's CRF, according to specific categories, as defined in section 18 of the protocol.

The device will be inspected, stimulation parameters setting will be re-evaluated and system performance parameters and usage information will be recorded in the CRF. Any change in OAB related medications or dosage will be recorded in the patient's CRF. During the 6- and 12- months follow-up visits quality of life (OAB-q) PGI-I and BSW questionnaires will be collected, as well as information on existence of mixed fecal and urine incontinence and severity of the fecal incontinence will be collected.

Sensory and motor thresholds will be assessed and recorded during each follow-up visit and leg circumference will be measured and recorded.

Specific activities and questionnaires associated with each follow-up visit is outlined on section 24; Study Schedule.

At the last visit, 12 months post activation, optimal treatment parameters and treatment regimen will be determined and adjusted on the device.

Number	Revision / Date	Page
G02-CLP-0002_US	Rev. 08 / 27 July 2021	45 of 75

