11.4.6 BlueWind RENOVA iStim™ System Long-Term Follow Up (LTF) Visits – Visits 9-12

Long term follow-up visits will be performed at 18, 24, 30, 36-months post activation.

If a subject already completed the 12-months follow-up and exited the study, she will be invited for a Long-Term Follow-Up Consent Visit in which, following her consent to participate in the long-term follow-up study, some eligibility criteria will be verified and treatment parameters setting will be performed. Subjects will enter the visit schedule using their original system activation date. Any visit that has already passed will not be counted as a missed visit.

If the subject discontinued treating herself when she exited the study and is activated again she will be asked to treat herself for 30 minutes, twice a day, for at least 4 weeks prior to completing the first LTF visit. During this period, she will be asked to complete a modified daily diary to capture incontinence episodes, time to treatment effect, and symptom improvement questions.

Subjects continuing to the long-term follow-up will be asked to treat themselves per physician discretion but not less than two 30-minute treatment per week.

All follow-up visits will require completion of 3-day voiding diary by the patient before coming to visit.

Follow-up visits 10 (24-months) and 12 (36-months) will be performed in clinic and will be similar to the 6 and 12-months follow-up visits

Follow-up visits 9 and 11 will be performed over a phone call unless the treatment is not effective enough or treatment parameters are not optimal or patient is experiencing an AE or device malfunction. In such cases the patient will arrive to the clinic and a visit similar to the 1, 3, and 9- months post activation will be performed.

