8.2 Primary Efficacy Endpoints

Document ID	Revision / Date	Page
G02-CLP-0009	Rev. 06 / 18 May 2022	12 of 26

The study's primary efficacy endpoint for each subject is response at 6 months post system activation as demonstrated by ≥50% improvement in the average number of urgency-related incontinence episodes as compared to baseline, measured by 7-day Patient Voiding Diary. Specifically, the primary endpoint will be defined as follows:

Success ("1") If the percent change from baseline to 6 months post system

activation in urgency-related incontinence episodes ≥50%

Failure ("0") Otherwise

Where the percent change from baseline to 6 months post system activation in urgency-related incontinence episodes is calculated as follows:

Document ID	Revision / Date	Page
G02-CLP-0009	Rev. 06 / 18 May 2022	13 of 26

$$\% \ Change_{BL \ to \ 6-months} = \frac{Episodes_{Avg. \ at \ BL} - \ Episodes_{Avg. \ at \ 6-months}}{Episodes_{BL}} * 100\%$$

where the average number of episodes is the average number of urgency-related leaks per day over the 7- day voiding diary. In the case that fewer than 5 days of diary data are available, then the average number of episodes for the given time point will be considered missing and, consequently, the primary endpoint will also be considered missing.

For the primary efficacy analysis, missing data will be addressed using the multiple imputation (MI) method, described above (Section 7.1).

Note: continuous score will be MI-imputed, and then the response is defined.

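### The descriptive dry rate rests on 3 unspecified consecutive diary days although 7 are collected at 6 and 12 months, so a woman with leaks in the same diary can be reported as dry

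*Protocol*

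**What the plan says.** - **Definition.** Protocol 10.3.3 lists the "Proportion of dry subjects following treatment with the RENOVA iStim System as measured by 3" "consecutive days of a patient voiding diary". The synopsis, Protocol 13.5.6 and SAP 8.4 and 12.6.3 use the same 3-day rule.
- **Time points and status.** Protocol 10.3.3 states: "The following endpoints will be assessed as other endpoints for the 6-, 12-, 24- and 36-months post activation, without formal hypothesis testing and type I" (the words cut off here refer to control of the type I error). SAP 12.6.3 treats the additional endpoints descriptively.
- **Diary length.** Protocol 11.4.5 asks for "a 7-day diary at the 6- and 12-months visits". For the long-term visits, Protocol 11.4.6 states: "All follow-up visits will require completion of 3-day voiding diary by the patient before coming to visit".
- **Contrast with the primary endpoint.** SAP 8.2 uses the "average number of urgency-related leaks per day over the 7- day voiding diary" and sets the value to missing when fewer than 5 days are available.
- **Meaning of dry.** The only gloss is in the pilot description, Protocol 7.2: "dry subjects (no episodes of leakage) were considered as 100% clinical improvement". The pilot used a 3-day diary.
- **Calculation rules.** SAP 8.4 refers to an appendix for diary calculations. Appendix 2 defers them until some time before database lock.

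**The concern.** At 6 and 12 months the endpoint discards four of the seven days collected. A woman can have leaks on the unused days, count as leaking in the primary endpoint, and still appear in the dry rate from the same diary. The choice of three days is also open. The trial is open label and the rule is not yet written, so it could be settled after the data have been seen.

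What is at stake is how the complete-continence figure is read. Readers and patients grasp such a figure easily, and the protocol's own risk-benefit section cites the earlier equivalent. A rate that includes women with recorded leaks says less than it appears to say.

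**Working it through.** The documents give no dry rate or misclassification rate for this trial, so there is no planned figure to reproduce.

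**Inputs.** The windows of 3 and 7 days come from Protocol 10.3.3 and 11.4.5. The leak rate of 2 per week is an assumption. For scale, entry requires urgency incontinence "defined as a minimum of nine (9) leaking episodes associated with urgency, with at least one episode per day for 5 days". A woman who enters at 9 per week and falls to 2 has improved by (9 − 2)/9 = 78%. She is a primary responder but not continent.

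**Step 1: direction.** With a complete 7-day diary, every woman dry on all 7 days is also dry on any 3 of them. The 3-day rate can therefore never be below the 7-day rate, whatever the leak distribution.

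**Step 2: size under independent Poisson leaks.** P(no leak in d days) = exp(−w·d/7), where w is the weekly rate.

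| w per week | fixed 3 days | all 7 days |
|---|---|---|
| 1 | exp(−3/7) = 65.1% | exp(−1) = 36.8% |
| 2 | exp(−6/7) = 42.4% | exp(−2) = 13.5% |
| 3 | exp(−9/7) = 27.6% | exp(−3) = 5.0% |

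**Step 3: clustered leaks.** With a gamma-mixed Poisson of shape k, P = (1 + w·d/(7k))^(−k). At w = 2:

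| k | fixed 3 days | all 7 days |
|---|---|---|
| 2 | 49.0% | 25.0% |
| 1 | 53.8% | 33.3% |
| 0.5 | 60.7% | 44.7% |

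The gap shrinks from about 29 to 16 percentage points but does not close.

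**Step 4: no rate model.** Suppose there are exactly 2 leak days in the week and all 21 patterns are equally likely. A fixed 3-day window is dry in C(4,2)/C(7,2) = 6/21 = 28.6% of patterns; the 7-day rule is never met.

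**Step 5: what the open rule could add.** Suppose any run of 3 dry days sufficed. Let q = exp(−2/7) = 0.7515 and p = 1 − q = 0.2485, so q³ = 0.4244. Then P = q³[1 + 3p + p(1 − q³)] = 0.4244 × 1.8886 = 80.1%. With exactly 2 leak days it is 18/21 = 85.7%. At 1 leak per week the Poisson figure is 94.2%.

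**Step 6: incomplete diaries.** At w = 2, a 5-day diary is leak-free with probability exp(−10/7) = 24.0%, against 13.5% for 7 days. Applying the primary endpoint's 5-day minimum here would make shorter diaries easier to call dry.

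**The case against.** The strongest defence is that a 3-day rule makes the four time points comparable. The 24- and 36-month diaries are only 3 days long, and the pilot, which reported 27.6% of 29 women dry, also used a 3-day diary. On a fixed window, dry means the same at 6, 12, 24 and 36 months, whereas a 7-day rate would not. The window is disclosed in the endpoint's wording, the full-diary leak count is reported alongside it, and the endpoint carries no formal inference. Much of this stands, although the documents do not give comparability as the reason. It supports keeping a 3-day rate; it does not support having no 7-day rate, or leaving the window unstated.

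A reader might go further and infer that the plan counts the best 3 days of 7, so that about 80% of women leaking twice a week would be called dry and the 6- and 12-month rates could not be compared with later ones. The documents do not support that. No section says that any 3 consecutive days suffice, and both conclusions depend on that reading. It shows what the missing rule leaves possible, not what is planned.

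It is also fair to say that these are classification probabilities at assumed leak rates. The overstatement in the trial's dry rate depends on the distribution of leak rates at 6 and 12 months, which the documents do not give.

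**Conclusion.** The point holds as a limited one. The dry endpoint leaves four collected days unused at 6 and 12 months and does not say which three it uses, so women with recorded leaks can be reported as dry. At an assumed 2 leaks per week the chance of being called dry is 42% on a fixed 3-day window against 13.5% on 7 days with independent leaks, and 61% against 45% with strong clustering. The direction needs no model; the size rests on the assumed rate and distribution. Seven days reduce the misclassification without removing it.

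Nothing here reaches the primary or secondary endpoints, the sample size or the success criterion. The change is worth making because it is cheap and the figure is easily over-read.

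**What to change.** In SAP 8.4 and Appendix 2, before the data are examined:

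1. At 6 and 12 months, report the proportion with zero leaks on all 7 diary days.
2. Count any recorded leak as not dry, even in an incomplete diary. Treat an incomplete diary with no leaks as missing, or show it separately by number of days recorded. SAP 7.1 does not impute additional endpoints, so give the number of such women: setting them aside while counting incomplete diaries with leaks pulls the rate down slightly.
3. State whether dry means no urgency leaks or no leaks of any kind. The diary also records stress leaks.
4. Keep a 3-day dry rate on a window fixed in advance, for example the first 3 diary days, for comparison with the 24- and 36-month diaries and the pilot.

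The cost is SAP wording and one extra table row per visit, with no new data, visits or patient burden. The downside for the sponsor is that the 7-day dry rate will be less favourable than the 3-day rate.

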10.4 Medication Usage

If used, patients should be on stable dose of OAB related medication (i.e. antimuscarinics and/or beta-3 adrenergic agonists for at least 3 months prior to baseline and agree to remain on stable medication consumption until the 12-month follow-up visit.

If used, patients should be on a stable dose of tricyclic antidepressants, Selective Serotonin Reuptake Inhibitors (SSRI) and Serotonin-Norepinephrine Reuptake Inhibitors (SNRI)) for at least 3 months prior to baseline.

Type and dosage of OAB related medications as well as any change in consumption during the study will be recorded in the CRF. All other medication consumption will be recorded in the CRF during the baseline visit and tracked 3 months back.

Number	Revision / Date	Page
G02-CLP-0002_US	Rev. 08 / 27 July 2021	31 of 75

Patients should avoid any OAB intervention (such as PTNS, SNM, or other neuromodulation treatments, Botox injections, surgical procedures, etc.) that may have an effect on overall study results throughout the 36 months follow-up period.

10.4.1 Allowed/disallowed medication

Patients will be administered prophylactic antibiotic and anti-inflammatory medications peri-operative (per section 11.4.2).

10.4.2 Documentation of concomitant medication

Any of the following concomitant medication consumption and dosages will be recorded in the CRF: Antibiotics, diuretics, anti-inflammatory, psychiatric medication, medication used to treat adverse events, cardiac, renal and endocrinology medication and any other medication that might affect urine output.

If there is a medical requirement to change OAB, diuretics or antidepressant medication during the study, these changes will be recorded and the patient will continue the study as planned.

10.5 Measurements

The clinical investigation variables will be assessed at baseline and/or at follow up visits using the following instruments:

- Voiding diary (7 day or 3 day): includes measurements of frequency, urgency, number of leaking episodes, leaks severity /amount leaked, and fluid consumed
- Quality of life questionnaire (OAB-q)
- Patient Global Impression of Improvement (PGI-I)
- Treatment Benefit, Satisfaction, and Willingness to Continue (BSW) questionnaire

10.6 Study Population

10.6.1 Patient Population

Women suffering from overactive bladder (OAB), including symptoms of urinary urgency incontinence (UUI).

10.6.2 Number of Subjects

One hundred fifty (150) subjects will be enrolled into the study to test the primary objective hypothesis (taking into account for up to 15% attrition).

10.7 Eligibility Criteria

10.7.1 Inclusion Criteria

1. Signed written informed consent.

Number	Revision / Date	Page
G02-CLP-0002_US	Rev. 08 / 27 July 2021	32 of 75

- 2. Female aged 18 or greater (21 or greater in the US), with no plans to become pregnant during the trial; if of bearing potential, negative pregnancy test and if sexually active, using acceptable contraception.
- 3. Subject who is mentally competent with the ability to understand and comply with the requirements of the study.
- 4. Diagnosis of UUI demonstrated on a 7-consecutive days voiding diary defined as a minimum of nine (9) leaking episodes associated with urgency, with at least one episode per day for 5 days.
- 5. More than or equal to 6 months history of UUI diagnosis
- 6. Subject with inadequate response to any of the following conservative treatments (i.e. dietary restriction, fluid restriction, bladder training, behavioral modification, pelvic muscle training, biofeedback, etc.) and pharmacologic treatment.
- 7. If used, subjects should be on stable dose of antimuscarinics and/or beta-3 adrenergic agonists for at least 3 months prior to baseline and agree to remain on stable medication consumption until the 12-month follow-up visit.
- 8. If used, subjects should be on a stable dose of tricyclic antidepressants, Selective Serotonin Reuptake Inhibitors (SSRI) and Serotonin-Norepinephrine Reuptake Inhibitors (SNRI) for at least 3 months prior to baseline.
- 9. Subjects with positive tibial nerve motor or sensory response tested via physical/neurological examination.
- 10. Subjects with normal renal function defined by GFR of 50 ml/min or more
- 11. Leg circumference of no less than 20 cm and no more than 30 cm at implantation site (i.e. 5cm above the medial malleolus).
- 12. Subject agrees to attend all follow-up evaluations and is willing and capable to completely and accurately fill out voiding diaries and questionnaires and is willing to complete required exams and tests.

The following inclusion criteria will be re-evaluated for patients who completed 12-months follow-up and exited the study:

1. Subject who is mentally competent with the ability to understand and comply with the requirements of the study.

